9.3.7 Safety Follow-up Phone Call (Week 16 or Early Termination)

A safety follow-up phone call will be made 28 days (±7 days) after withdrawal from the study or after completion of the study. A concomitant medication and AE assessment will be completed.

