A safety follow-up phone call will be made 4 weeks after completion of the 12 weeks of treatment. Subjects who discontinue or who are withdrawn prior to study completion will come to the site for an Early Termination Visit as soon as possible and will be contacted for a safety follow-up 4 weeks after the last dose of study medication.

Enrollment caps may be implemented throughout the course of the study based on the patient reported outcome (ie, PHQ-9 and PDQ-D) scores at Baseline.

A futility analysis may be performed at an interim analysis after approximately 60 subjects have completed the study.

- (a) Recommended starting dosage is 10 mg/day as ideal dosage. Dosage may be decreased to 5 mg/day at discretion of the investigator or designee.
- (b) If all screening activities are completed and the subject meets the eligibility criteria the Screening and Baseline Visits can be combined into 1 visit.
- (c) Subjects currently on an antidepressant at Screening will be discontinued in a manner that is consistent with labeling recommendations and conventional medical practice prior to Baseline.

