9.1.9 Contraception and Pregnancy Avoidance Procedure

From signing of informed consent, throughout the duration of the study, and for 30 days after last dose of study medication, female subjects of childbearing potential must use adequate contraception. In addition, they must be advised not to donate ova during this period.

*Females NOT of childbearing potential are defined as those who have been surgically sterilized (hysterectomy, bilateral oophorectomy or tubal ligation) or who are postmenopausal (eg, defined as at least 1 year since last regular menses with a FSH>40 IU/L or at least 5 years since last regular menses, confirmed before any study medication is implemented).

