9.1.10 Pregnancy

If any subject is found to be pregnant during the study she should be withdrawn and any sponsor-supplied drug should be immediately discontinued.

If the pregnancy occurs during administration of active study medication, eg, after Visit 2 or within 30 days of the last dose of active study medication, the pregnancy should be reported immediately, using a pregnancy notification form, to the contact listed in Section 1.1.

Should the pregnancy occur during or after administration of blinded drug, the investigator must inform the subject of their right to receive treatment information. If the subject chooses to receive unblinded treatment information, the individual blind should be broken by the investigator.

If the female subject agrees to the primary care physician being informed, the investigator should notify the primary care physician that the subject was participating in a clinical study at the time she became pregnant and provide details of treatment the subject received.

All reported pregnancies will be followed up to final outcome, using the pregnancy form. The outcome, including any premature termination, must be reported to the sponsor. An evaluation after the birth of the child will also be conducted.

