10.2 Procedures

10.2.1 Collection and Reporting of AEs

10.2.1.1 PTE and AE Collection Period

Collection of PTEs will commence from the time the subject signs the informed consent to participate in the study and continue until the subject is first administered study drug (Baseline Visit 1) or until screen failure. For subjects who discontinue prior to study drug administration, PTEs are collected until the subject discontinues study participation.

Collection of AEs will commence from the time that the subject is first administered study drug (Baseline Visit 1). Routine collection of AEs will continue for 4 weeks post the last dose of study medication.

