7.9 Safety Analysis

7.9.1 Adverse Events

All adverse events will be coded using the latest version of MedDRA. In this dictionary, each verbatim term is coded to a lower level term, and then mapped to a preferred MedDRA term, which is then mapped to an SOC. All adverse events from the safety analysis set will be included in the data listings but only treatment-emergent adverse events will be included in the summary tables.

A treatment-emergent adverse event (TEAE) is defined as an adverse event with an onset that occurs after receiving study drug (AE start date \geq first dose date) and within 30 days after receiving the last dose of study drug (AE start date – last dose date \leq 30). Adverse events with onset occurring more than 30 days after last dose of study drug (AE start date – last dose date $>$ 30) will be listed, but not included in the summary tables. Adverse events with missing onset dates will be summarized regardless of severity and relationship to study medication.

Serious adverse events (SAEs) with onset that occurs after receiving study drug (AE start date \geq first dose date) and within 30 days after receiving the last dose of study drug (AE start date - last dose date \leq 30) will be summarized.

In the high-level adverse event summary tables, TEAEs will be summarized regardless of intensity and relationship to study drug. Within each subject, multiple reports of events that map to a common MedDRA term will be counted only once for calculating incidence rates.

At the adverse event level, the summary tables will present the number of subjects reporting each of these MedDRA events, ie, the numbers of subjects reporting 1 or more events that map to the given MedDRA term.

At the SOC level, the summary tables will present the number of subjects reporting 1 or more events that map to the given SOC. That is, the number of subjects reported at the SOC level will be less than or equal to the sum of the subject counts across all adverse events within that SOC.

In selected summaries (TEAEs overview, and TEAEs by SOC and preferred term), adverse events will be summarized by the number of events reported in addition to the number and percentage of subjects with at least one event.

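### Post-treatment safety windows disagree: the only scheduled call may fall at day 21, but AEs are collected to 4 weeks and TEAEs counted to 30 days after last dose

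*Protocol*

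**What the plan says.** Several passages set an end to the same post-treatment period.

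- **AE collection.** Protocol 10.2.1.1: "Routine collection of AEs will continue for 4 weeks post the last dose of study medication".
- **TEAE and SAE counting.** SAP 7.9.1 includes events with onset from first dose and "within 30 days after receiving the last dose of study drug". Later events are listed but not tabulated.
- **Pregnancy.** Protocol 9.1.10 requires reporting of a pregnancy that occurs "within 30 days of the last dose of active study medication", and 9.1.9 requires contraception "for 30 days after last dose of study medication".
- **The call, body text.** Protocol 9.3.7: "A safety follow-up phone call will be made 28 days (±7 days) after withdrawal from the study or after completion of the study". Its content is one sentence: "A concomitant medication and AE assessment will be completed".
- **The call, design section.** Protocol 6.1 places it 4 weeks after the 12 weeks of treatment for completers. Early discontinuers "will be contacted for a safety follow-up 4 weeks after the last dose of study medication". Neither statement has a tolerance.
- **The call, schedule.** Appendix A puts Visit 8 at Day 113 ± 7, counted from Day 1, with Visit 7 at Day 85 ± 5.

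Appendix A shows no other contact after Week 12/Early Termination, and no passage asks for a second contact when the call is made early.

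**The concern.** The collection period, the tabulated period and the timing of the call use different lengths (4 weeks, 30 days, 28 ± 7 days). They also use different starting points: last dose, withdrawal or completion, and Day 1. A site can follow 9.3.7 exactly and stop asking a subject about AEs before either the Protocol's or the SAP's window has closed, while another subject is asked about the whole of it. Events after drug stops would then enter the TEAE tables partly according to the date of the call, and the SAP neither flags nor handles this.

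Days 29 and 30 raise a separate problem. The SAP tabulates them, but they lie outside the Protocol's routine collection. Under Protocol 10.2.2, an SAE that reaches the investigator after the collection period goes to the sponsor only if it is reported spontaneously and considered related to study participation. The SAP's SAE summary makes no such distinction.

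For pregnancy, the last scheduled test is at Week 12/Early Termination and the listed content of the call does not mention pregnancy. Safety and tolerability are among the additional objectives in Protocol 5.1.3.

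**Working it through.** **Inputs.** Call at 28 ± 7 days (Protocol 9.3.7); Visit 7 at Day 85 ± 5 and Visit 8 at Day 113 ± 7 (Appendix A); AE collection to 28 days after last dose (10.2.1.1); TEAE and SAE counting to 30 days after last dose (SAP 7.9.1); pregnancy reporting to 30 days (9.1.10). Assumption: last dose is at about the day of the final visit.

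**1. The schedule's own figures.** Week 12 is 12 × 7 + 1 = Day 85 and Week 16 is 16 × 7 + 1 = Day 113. The nominal gap is 113 − 85 = 28 days, so Appendix A and 9.3.7 agree at the nominal dates.

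**2. Permitted call days under 9.3.7.** From 28 − 7 = 21 to 28 + 7 = 35, which is 15 days.

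| Call day | Short of 28 | Short of 30 |
|---|---|---|
| 21 | 7 | 9 |
| 28 | 0 | 2 |
| 30 | 0 | 0 |
| 35 | 0 | 0 |

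Days 21 to 27 precede day 28: 7 of 15 (47%). Days 21 to 29 precede day 30: 9 of 15 (60%). These are counts of permitted days, not forecasts of when calls will be made.

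**3. Average shortfall.** The documents give no distribution of call dates, so this is an illustration with its range. If calls were spread evenly over the 15 days, the mean unsolicited time up to day 30 is (9 + 8 + … + 1)/15 = 45/15 = 3.0 days per subject. If every call fell on day 28 it would be 2 days, if every call fell on day 21 it would be 9, and if none came before day 30 it would be 0.

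**4. Relative size.** TEAEs are counted from first dose, so for a 12-week completer the period is about 84 + 30 = 114 days. The even-spread shortfall is 3.0/114 = 2.6% of it, and the largest under 9.3.7 is 9/114 = 7.9%.

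**5. Different anchors.** If last dose precedes the final visit by d days, a day-21 call falls 21 + d days after last dose and the shortfall to day 30 is 9 − d, with a floor of 0.

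**6. Appendix A read alone.** The smallest gap between Visit 7 and Visit 8 is (113 − 7) − (85 + 5) = 106 − 90 = 16 days, and the largest is (113 + 7) − (85 − 5) = 120 − 80 = 40 days. Both lie outside the 21 to 35 days of 9.3.7. Of the 11 × 15 = 165 permitted pairs of visit days, 1 + 2 + 3 + 4 + 5 = 15 (9%) give a gap below 21 days.

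**The case against.** The best defence is that little is lost. Subjects may report AEs at any other time during the study (Protocol 10.2.1.2), and unscheduled visits with an AE assessment are allowed at any time after Week 2 (9.3.6). Collection formally runs its 4 weeks whatever the date of the call. Related SAEs reported later still reach the sponsor. There is one arm, so no between-arm comparison can be biased, and Protocol 13.1.4 plans no inferential safety statistics. All of this stands. It limits the consequence, but it does not make the passages agree, and passive reporting is not the same as asking.

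A reader might infer more than the documents support in four ways:

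- **That the TEAE tables give a 30-day post-dose incidence.** They do not. The planned tables pool treatment and follow-up, so the shortfall should be set against about 114 days, not 30.
- **That a call 16 days after the final visit complies with the plan.** It meets Appendix A but breaks the 21-day minimum in 9.3.7. It shows that those two passages also need reconciling.
- **That late events go uncollected.** Only active solicitation ends at the call.
- **That the Protocol promises to detect pregnancies to day 30.** Section 9.1.10 sets a duty to report, not a schedule of testing or questioning. The fair point is narrower: the reporting window and the listed content of the call do not match.

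**Conclusion.** The inconsistency is real and minor. A call that follows 9.3.7 can end solicited AE collection up to 7 days before the Protocol's window closes and up to 9 days before the SAP's, and a punctual day-28 call leaves 2 days of the SAP's window unsolicited. Under an even spread of calls the average is about 3 days per subject, or 2.6% of a completer's TEAE period. These figures assume that last dose coincides roughly with the final visit and that completion in 9.3.7 means that visit. An earlier last dose shrinks them. The primary endpoint is unaffected. What suffers is the uniformity of follow-up behind the TEAE and SAE tables.

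**What to change.** Reconcile Protocol 6.1, 9.1.10, 9.3.7, 10.2.1.1, Appendix A and SAP 7.9.1 to one anchor, last dose, and one end-day, and carry the change into the copies of the 6.1 text in Protocol 2.0 and SAP 4.4. The test of success is that, for every subject whose call complies with the plan, the scheduled contact covers the whole period the SAP tabulates. The sponsor chooses the end-day and the call window. This can be done by changing the call timing, the SAP cut-off, or both. Make Appendix A and 9.3.7 give the same permitted range. Also reconcile the 30-day pregnancy reporting window with the listed content of the call, which is now concomitant medication and AEs only.

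The cost is wording in the Protocol and SAP, with no added contact. Some calls, or the SAP cut-off, would move by a few days, and if calls move later a few more subjects may be hard to reach.

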9.3.8 Poststudy Care

Sponsor-supplied drug will not be available upon completion of the subject's participation in the study. The subject should be returned to the care of a physician and standard therapies as required.

9.4 PGx Sample Retention and Destruction

In this study, specimens for genome/gene analysis will be collected as described in Section 9.1.11. The genetic material will be preserved, retained, and initially stored at PPD Central Laboratory and then preserved and retained for long-term storage at Covance Central Laboratory or as required by applicable law. The sponsor has put into place a system to protect the subjects' personal information to ensure optimal confidentiality and defined standard processes for sample and data collection, storage, analysis, and destruction.

The sample will be labeled with a unique sample identifier similar to labeling in the main study but using a code that is different from the code attached to the health information and other clinical test results collected in the study. The sample and data are linked to personal health information with code numbers. This link means that the subject may be identified but only indirectly. The code numbers will be kept secure by or on behalf of the sponsor.

Subjects who consented and provided a PGx sample for DNA and RNA analysis can withdraw their consent and request disposal of a stored sample at any time. Sponsor must be notified of the consent withdrawal.

10.0 PRETREATMENT EVENTS AND ADVERSE EVENTS

10.1 Definitions

10.1.1 PTEs

A PTE is defined as any untoward medical occurrence in a clinical investigation subject who has signed informed consent to participate in a study but prior to administration of any study drug; it does not necessarily have to have a causal relationship with study participation.

10.1.2 AEs

An AE is defined as any untoward medical occurrence in a clinical investigation subject administered a drug; it does not necessarily have to have a causal relationship with this treatment.

An AE can therefore be any unfavorable and unintended sign (eg, a clinically significant abnormal laboratory value), symptom, or disease temporally associated with the use of a drug whether or not it is considered related to the drug.

10.1.3 Additional Points to Consider for PTEs and AEs

An untoward finding generally may:

- Indicate a new diagnosis or unexpected worsening of a pre-existing condition. (Intermittent events for pre-existing conditions or underlying disease should not be considered PTEs or AEs.)
- Necessitate therapeutic intervention.
- Require an invasive diagnostic procedure.
- Require discontinuation or a change in dose of study drug or a concomitant medication.
- Be considered unfavorable by the investigator for any reason.
- PTEs/AEs caused by a study procedure (eg, a bruise after blood draw) should be recorded as a PTE/AE eCRF page.

Diagnoses vs signs and symptoms:

• Each event should be recorded to represent a single diagnosis. Accompanying signs (including abnormal laboratory values or electrocardiogram [ECG] findings) or symptoms should NOT be recorded as additional AEs. If a diagnosis is unknown, sign(s) or symptom(s) should be recorded appropriately as a PTE(s) or as an AE(s).

Laboratory values and ECG findings:

• Changes in laboratory values or ECG findings are only considered to be PTEs or AEs if they are judged to be clinically significant (ie, if some action or intervention is required or if the investigator judges the change to be beyond the range of normal physiologic fluctuation). A

- laboratory or ECG re-test and/or continued monitoring of an abnormal value or finding are not considered an intervention. In addition, repeated or additional noninvasive testing for verification, evaluation or monitoring of an abnormality is not considered an intervention.
- If abnormal laboratory values or ECG findings are the result of pathology for which there is an overall diagnosis (eg, increased creatinine in renal failure), the diagnosis only should be reported appropriately as a PTE or as an AE.

Pre-existing conditions:

- Pre-existing conditions (present at the time of signing of informed consent) are considered concurrent medical conditions and should NOT be recorded as PTEs or AEs. Baseline evaluations (eg, laboratory tests, ECG, X-rays) should NOT be recorded as PTEs unless related to study procedures. However, if the subject experiences a worsening or complication of such a concurrent medical condition, the worsening or complication should be recorded appropriately as a PTE (worsening or complication occurs before start of study drug) or an AE (worsening or complication occurs after start of study drug). Investigators should ensure that the event term recorded captures the change in the condition (eg, "worsening of...").
- If a subject has a pre-existing episodic concurrent medical condition (eg, asthma, epilepsy) any occurrence of an episode should only be captured as a PTE/AE if the condition becomes more frequent, serious, or severe in nature. Investigators should ensure that the AE term recorded captures the change in the condition from Baseline (eg "worsening of...").
- If a subject has a degenerative concurrent medical condition (eg, cataracts, rheumatoid arthritis), worsening of the condition should only be recorded as a PTE/AE if occurring to a greater extent to that which would be expected. Investigators should ensure that the AE term recorded captures the change in the condition (eg, "worsening of...").

Worsening of PTEs or AEs:

- If the subject experiences a worsening or complication of a PTE after the start of study drug, the worsening or complication should be recorded as an AE. Investigators should ensure that the AE term recorded captures the change in the PTE (eg, "worsening of...").
- If the subject experiences a worsening or complication of an AE after any change in study drug, the worsening or complication should be recorded as a new AE. Investigators should ensure that the AE term recorded captures the change in the condition (eg, "worsening of...").

Changes in intensity of AEs /Serious PTEs:

• If the subject experiences changes in intensity of an AE/serious PTE, the event should be captured once with the maximum intensity recorded.

Preplanned procedures (surgeries or interventions):

• Preplanned procedures (surgeries or therapies) that were scheduled prior to signing of informed consent are not considered PTEs or AEs. However, if a preplanned procedure is performed early (eg, as an emergency) due to a worsening of the pre-existing condition, the

worsening of the condition should be recorded as a PTE or an AE. Complications resulting from any planned surgery should be reported as AEs.

Elective surgeries or procedures:

• Elective procedures performed where there is no change in the subject's medical condition should not be recorded as PTEs or AEs, but should be documented in the subject's source documents. Complications resulting from an elective surgery should be reported as AEs.

Insufficient clinical response (lack of effectiveness):

• Insufficient clinical response, effectiveness, or pharmacologic action, should NOT be recorded as an AE. The investigator must make the distinction between exacerbation of pre-existing illness and lack of therapeutic effectiveness.

Overdose:

 Cases of overdose with any medication without manifested side effects are NOT considered PTEs or AEs, but instead will be documented on an Overdose page of the eCRF. Any manifested side effects will be considered PTEs or AEs and will be recorded on the AE page of the eCRF.

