10.1.9 Start Date

The start date of the AE/PTE is the date that the first signs/symptoms were noted by the subject and/or investigator.

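### Protocol 10.1.3 has two overlapping rules for recording an event that worsens on treatment and does not say which prevails, so a serious pretreatment event that worsens after first dose can be left out of the TEAE and SAE tables

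*Protocol*

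**What the plan says.** Two neighbouring rules in Protocol 10.1.3 deal with an event that gets worse.

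- *Worsening of PTEs or AEs.* For a PTE: "worsening or complication of a PTE after the start of study drug, the worsening or complication should be recorded as an AE". For an AE: "worsening or complication of an AE after any change in study drug, the worsening or complication should be recorded as a new AE". Sites are also asked to word the event term so that it shows the change.
- *Changes in intensity of AEs /Serious PTEs.* Here the instruction is to keep one record: "If the subject experiences changes in intensity of an AE/serious PTE, the event should be captured once with the maximum intensity recorded". This rule covers AEs and serious PTEs, does not mention nonserious PTEs, and makes no exception for starting or changing study drug.

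Protocol 10.1.9 dates every record from its beginning: "The start date of the AE/PTE is the date that the first signs/symptoms were noted by the subject and/or investigator".

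SAP 7.9.1 then selects events by that date: "A treatment-emergent adverse event (TEAE) is defined as an adverse event with an onset that occurs after receiving study drug", up to 30 days after the last dose. The SAE table uses the same window: "Serious adverse events (SAEs) with onset that occurs after receiving study drug". Neither definition mentions an event that began before dosing and worsened afterwards. On counting, the SAP says: "Within each subject, multiple reports of events that map to a common MedDRA term will be counted only once for calculating incidence rates". The TEAE overview and the table by SOC and preferred term also report numbers of events.

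**The concern.** A worsening is ordinarily a rise in intensity, so two kinds of event fall under both rules: a serious PTE that worsens after the first dose, and an AE that worsens after a dose change. One rule gives a separate record and the other gives a single one. About 25 sites would each have to choose.

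The first kind matters more. If the site keeps one record, the start date lies before the first dose and the event fails the SAP's onset test. The subject is then missing from the TEAE table and the treatment-emergent SAE table. If the worsening led to withdrawal, the subject is also missing from the table of TEAEs leading to discontinuation, although AEs leading to discontinuation are a named safety assessment (Protocol 5.3). In addition, Protocol 10.2.1.2 does not collect relationship to study drug or action taken for PTEs, so a worsening kept on a PTE record has neither entry on that eCRF page. The separate SAE form does ask for causality (10.2.2).

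For the second kind, the protocol provides for dose increases as tolerated (6.2.2, 8.2), so changes in study drug are expected.

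**Working it through.** The plan states no figure on this point, so there is nothing to reproduce. The check applies the SAP's date rule to four illustrative events, each recorded first under the worsening rule and then under the single-record rule.

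**Rule (SAP 7.9.1).** A record is a TEAE if start date ≥ first dose date and start date − last dose date ≤ 30.

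**Assumed days.** First dose Day 1, last dose Day 85 (the scheduled Week 12 day), PTE onset Day −5, AE onset Day 10, worsening Day 20. A separate record is dated from the worsening; a single record is dated from the first signs (10.1.9).

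**Date test.**
- Day −5: −5 < 1, so not a TEAE.
- Day 10: 10 ≥ 1 and 10 − 85 = −75 ≤ 30, so a TEAE.
- Day 20: 20 ≥ 1 and 20 − 85 = −65 ≤ 30, so a TEAE.

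| Event | Worsening rule: TEAE records | Single-record rule: TEAE records | Subject in TEAE table under single-record rule? |
|---|---|---|---|
| Nonserious PTE, worsens Day 20 | 1 | 1 (rule does not apply) | Yes |
| Serious PTE, worsens Day 20 | 1 | 0 | **No** |
| AE from Day 10, worsens after dose change Day 20 | 2 | 1 | Yes |
| AE from Day 10, worsens and becomes serious after dose change Day 20 | 2 | 1 | Yes, and in the SAE table if the record is flagged serious |

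Only the second row loses a subject. In the third and fourth rows the original onset already meets the TEAE definition. The SAP counts the subject once per term and at maximum intensity, so one record or two gives the same incidence and intensity entries. The number of events and the date of worsening differ.

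One borderline case is not settled by the text: a PTE that is nonserious before dosing and becomes serious only on drug. The protocol does not say whether the single-record rule then covers it.

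**Check on a possible SAP remedy.** Suppose the TEAE definition also admitted any PTE that worsens after first dose, while the protocol still creates a separate AE. In the second row both the Day −5 record and the Day 20 record would then qualify, giving 2 records for one worsening.

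**The case against.** The strongest reply is that the two rules can be read together. Protocol 10.1.1 confines a PTE to the time before any study drug, and 10.2.1.1 ends PTE collection and begins AE collection at first dose. A worsening after that point therefore belongs to the AE period. Protocol 10.1.3 draws the same line for pre-existing conditions. The specific trigger, a start of or change in study drug, would then govern, and the single-record rule would cover fluctuation without such a trigger. Nor does that rule say that the single record must be the pretreatment one. This is a sensible reading and probably what was meant. But it is not written, and the heading of the single-record rule names serious PTEs without any exception.

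The reply also holds that the affected case is narrow. Screening lasts at most 21 days and may be combined with Baseline, clinically significant unstable illness is excluded, and a PTE is itself a listed reason for withdrawal. A subject would need a serious PTE, still be dosed, and then worsen. Even so, the event is reported as an SAE and appears in the PTE table and the listings. All of this stands.

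A reader might infer that worsenings on treatment in general drop out of the TEAE and SAE tables. The documents do not support that: an AE that began on drug is already treatment-emergent, and no planned AE table is broken down by dose. A reader might also try to size the problem by assuming, say, that 60% to 80% of 120 subjects have a dose increase and 10% to 30% of those have an AE that worsens: 120 × 0.6 × 0.1 = 7.2 up to 120 × 0.8 × 0.3 = 28.8. Neither share is in the documents, and the result would count extra records, not subjects missing from a table.

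**Conclusion.** The point holds in a limited form. Two stated rules in Protocol 10.1.3 conflict, with no precedence given.

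- **Serious PTE that worsens after first dose:** literal use of the single-record rule, with 10.1.9 and the onset-only definitions in SAP 7.9.1, takes the event from 1 TEAE record to 0 and removes the subject's event from the TEAE and treatment-emergent SAE tables. It remains in the PTE table and listings. The documents give no rate of serious PTEs. The case is probably rare, but one omission would show in a small SAE table.
- **AE that began on drug and worsens after a dose change:** 2 records or 1. Subject-level incidence and maximum-intensity tables are unchanged, provided both records code to the same preferred term. Event counts in the selected summaries and the date of worsening depend on the site. No reliable frequency can be given.
- **Nonserious PTEs:** not affected, apart from the borderline case of one that becomes serious on drug.

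The primary endpoint is untouched, and AEs are summarised without inferential testing. The point is still worth acting on, because following one of the two rules as written gives a wrong safety table.

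**What to change.** - **Protocol 10.1.3, *Changes in intensity*.** Add: *This single-record rule applies only where no start of, or change in, study drug comes between the original event and the change in intensity. Otherwise the worsening is recorded as a separate AE, as stated above.*
- **Protocol 10.1.9.** Add: *For an AE that records a worsening, the start date is the date on which the worsening was first noted.*
- **eCRF completion guidance.** Carry the same two sentences.
- **SAP 7.9.1.** With these changes the onset-based TEAE and SAE definitions work as written. If a worsening clause is added as a safeguard, limit it to PTEs that have no separate post-dose AE record, to avoid the double count shown above.

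The cost is a few sentences of text. The downside is slightly higher TEAE event counts. The edits concern recording and tabulation only and do not change how any subject is managed.
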